5 STUDY DESIGN

The study will be an open label explorative, randomised, dose rising design, NAC controlled study in patients treated for paracetamol/acetaminophen overdose using the 12hr NAC regime.

Entry into the study will depend on the patient's blood results confirming need for NAC.

Patients that have signed the informed consent will be treated with NAC followed by rising doses of the PP100-01. Each PP100-01 treatment dosing cohort will have 8 patients, 6 randomised to PP100-01 and 2 randomised to NAC alone.

- Group A: PP100-01 (2 µmol/kg calmangafodipir) after the "loading" dose of NAC
- Group B: PP100-01 (5 µmol/kg calmangafodipir) after the "loading" dose of NAC
- Group C: PP100-01 (10 µmol/kg calmangafodipir) after the "loading" dose of NAC

PP100-01 treatment is administered intravenously during 5 minutes.

The standard NAC regime will be continued with the second dose: 200 mg/kg NAC in 1000 ml i.v. over 10hrs.

The patients will continue NAC treatment according to standardised guidelines throughout the study until the patient is considered normalized and can leave the hospital.

The study will primarily evaluate safety and tolerability for treatment with PP100-01 in combination with NAC compared to the 12hr NAC treatment regime.

6 STUDY POPULATION

6.1 Number of Participants

We aim to recruit a total of 24 patients presenting with POD and requiring treatment with NAC to the study. We approximate this can be completed in a 6-12 months recruitment period.

6.2 Inclusion Criteria

- 1. Any patient with capacity admitted to hospital within 24 hrs either a single acute POD or more than one dose of paracetamol (staggered) and deemed to require treatment with NAC.
- 2. Provision of written informed consent
- 3. Males and females of at least 16 years of age

These patients will include:

a) Patients presenting within 8h of overdose who have a timed blood paracetamol concentration above the 100-line on the UK APAP overdose treatment nomogram (See Figure 1).

b) Patients presenting later than 8h who are at risk of liver injury from the reported dose ingested and have blood results confirming need for NAC

c) Patients presenting after taking a staggered APAP overdose (defined as when the overdose of APAP is taken over a period of more than 1hr)

6.3 Exclusion Criteria

In order to participate in the study patients must not meet any of the following exclusion criteria:

- 1. Patients that do not have the capacity to consent to participate in the study
- 2. Patients detained under the Mental Health Act or deemed unfit by the Investigator to participate due to mental health.
- 3. Patients with known permanent cognitive impairment
- Patients who are pregnant or nursing
 Patients who have previously participated in the study
- 6. Unreliable history of POD
- 7. Patients presenting after 24hrs of POD
- 8. Patients who take anticoagulants (e.g. warfarin) therapeutically or have taken an overdose of anticoagulants

9. Patients who, in the opinion of the responsible clinician/nurse, are unlikely to complete the full course of NAC e.g. expressing wish to self-discharge

11. Non-English speaking patients. (Study information material will only be produced in English in view of the known and stable demographic of the Edinburgh self-harm population).

6.4 Participant Selection and Enrolment

6.4.1 Identifying Participants

Potentially eligible patients will be identified by treating clinicians at the Emergency Department of the Royal Infirmary of Edinburgh. They will inform an appropriately trained member of staff who will assess the patient for study eligibility. The Investigator or/and the study staff members who explains the study will ensure that the interview takes place without interruption and is responsible that the information is understood. The patient is encouraged to take time for reflection on the information presented before making a decision as to whether they wish to participate in the clinical study.

6.4.2 Consenting Participants

The patient will be given a Patient Information Sheet (PIS), which will explain the aims of the study and the potential risks and benefits of the study treatments.

The oral information will contain information on any foreseeable risks, side effects, complications and disadvantages, and that there may be unpredictable risks and discomforts associated with participation in a clinical study. The information shall also include information on any treatment that can be offered, if the patient chooses not to participate in the study. This information will also be given to the patient in writing in the Patient Information Sheet document.

The patient will be given enough time to consider the study and ask questions regarding their participation in the study. At most this could be about an hour but may be only 10-15 mins if the time lapse since APAP ingestion indicates a need to start treatment quickly.

If the patient wishes to participate in the study then the patient must sign the Informed Consent Form (ICF) before inclusion in the study. It is the Investigator's responsibility to ensure consent is obtained before any study specific procedures are carried out. Signing of the ICF occurs after the information has been received from both oral and written PIS. Both the patient and the person delegated to take consent will sign and personally date the ICF. The original signed ICF must be kept by the Investigator in the ISF, 1 copy is provided to the participant and 1 copy is placed in the medical file.

6.4.3 Assess Capacity

Capacity will be assessed by a doctor in the Emergency Department who has:

- completed GCP training (including specific training in assessing capacity)
- completed study specific training
- has been delegated this responsibility by the Principal Investigator

Only patients with capacity will be invited to participate in the study.

6.5 Screening for Eligibility

Patients where a clinical decision has been made to treat with NAC will be screened for eligibility to participate in the study and recorded on the screening log. The decision to treat with NAC will be made by the treating clinician based on protocols agreed by the National Poisons Information Service and available on TOXBASE, a web-based poisons information resource which is the UK national standard for therapy. Ineligible and non-recruited participants will be recorded on the screening log with a reason given.

At screening, age, sex and race will be recorded in the CRF for all patients.

All patients deemed eligible to take part in this study will be entered onto a Consent & Subject Status Log after consent and pre-screening checks are completed.

^{10.} Prisoners

6.6 Treatment Allocation

6.6.1 Treatment Allocation Procedure

Eligible patients will be allocated to treatment according to a rising dose design. Allocation of patients to each dose will need to be completed before allocation can start for the next dose. In each dosing cohort there will be 8 patients. 6 will receive PP100-01 and NAC and 2 NAC alone. There will be a randomisation process at entry to the study that will determine treatment allocation within dosing cohort.

- Group A: PP100-01 (2 µmol/kg calmangafodipir) after the "loading" dose of NAC
- Group B: PP100-01 (5 µmol/kg calmangafodipir) after the "loading" dose of NAC
- Group C: PP100-01 (10 µmol/kg calmangafodipir) after the "loading" dose of NAC

Once a patient is allocated a treatment number he/she will remain in the study and have all outcomes recorded, unless he/she specifically withdraws consent to have data stored.

All medical and nursing staff caring for the patient will know (open label) treatment allocation. PP100-01, specially prepared and packaged for clinical study purposes, will be prepared and labelled to patient allocation number. Stores of packs will be held within the hospital pharmacy and sufficient packs supplied to the Emergency Department as required.

Doses of NAC and PP100-01 are based on the patient's weight and therefore infusions need to be prepared individually for each patient. NAC will be prepared by the clinical team or a delegated member of the research team and PP100-01 by a delegated member of the research team according to the 'Site Instructions for handling the IMP'.

A period of 24 hours will be left between recruitment of the first participant allocated to PP100-01+NAC treatment in each dosing cohort and recruitment of the next participant to allow adequate time for early adverse events to be identified.

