6.7 Patient Replacement

Replacement of patients will be allowed in order to obtain the planned number of evaluable patients in each dosing cohort. Any patients that discontinue treatment for a reason other than Dose Limiting Toxicity (DLT) will be replaced.

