7.1.7 Treatment Phase

Treatment will start with the first NAC bag of 100 mg/kg in 200 ml ("loading dose") at time point '0'. Immediately prior to PP100-01 a study specific blood sample will be collected (time 2hr).

PP100-01 treatment is administered intravenously as a bolus infusion over 5 minutes at the dose specified by the dosing cohort:

- Group A: PP100-01 (2 µmol/kg calmangafodipir) after the "loading" dose of NAC
- Group B: PP100-01 (5 µmol/kg calmangafodipir) after the "loading" dose of NAC
- Group C: PP100-01 (10 µmol/kg calmangafodipir) after the "loading" dose of NAC

All necessary precautions will be taken during administration of the study drug. The patient will be monitored with vital signs (Section 7.1.3). Observation and medical treatment for anaphylactic shock will, as a standard be requisite.

The 12hr NAC regime will be continued with the second dose: 200 mg/kg NAC in 1000 ml i.v. over 10 hr. As per routine clinical practice, there will be one blood sample taken 2 hrs before the end of the second NAC bag (the 10hr time-point) and a second blood sample taken 10h later (the 20hr time-point).

The following procedures should be performed during the treatment phase at time-points: baseline, 2hr, 10hr and 20hr (see study schedule, section 7.2 (Table 1)):

• ALT, bilirubin and alkaline phosphatase (ALP)

- Prothrombin time and INR
- Serum creatinine
- Biomarkers: CK18 and microRNA MiR122, GLDH, mitochondrial DNA and others
- PP100-01 level will be assessed at 2hr, 10hr and 20hr

Any rescue medication given will be recorded in the Case Report Form by routine clinical staff.

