7.1.11 Assessment timelines

2, 2.5 hour assessments should be performed +/-15mins of the timepoint. PP100-01 treatment should be +/- 10mins of timepoint. 10, 20 hour assessments should be performed +/-30minutes of the timepoint.

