4.3 Adherence with allocated treatment (FA)

No formal statistical testing will be performed. The following will be summarised by treatment group and overall:

- Numbers of patients who were randomised but never treated with either NAC or PP100-01.
- NAC treatment
 - Time from ingestion of paracetamol to start of NAC treatment (hrs)
 - 12 hour NAC regimen
 - Completed without stopping
 - Completed with stop(s) and restart(s)
 - Stopped permanently during first infusion
 - Stopped permanently during second infusion
 - Not started
 - Percentage of intended dose received
(see Appendix 1 for weight-based lookup table for intended dose)
 - Number of additional NAC infusions after 12 hour regimen
(none / 1 / 2 / more than 2)
- PP100-01 treatment
 - Time from ingestion of paracetamol to start of PP100-01 treatment (hrs)
 - Bolus status
 - Completed
 - Stopped early
 - Not started
 - Percentage of intended dose received
 - PP100-01 level at 2, 10 and 20hrs

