4.9 Data listings

Consented patients

Data will be listed for those patients who, after having consented to participate, underwent baseline examinations required for inclusion into the study but who, because a criterion for exclusion was met or for other reasons, were not included in the study. Patient ID and reason(s) for exclusion will be listed.

Withdrawals

Patient ID and all reasons for withdrawal will be listed for patients who have withdrawn from the study.

Medical History (FA)

Medical history will be presented in a line listing, ordered by treatment group and patient ID, of the descriptive text of each event/condition and whether it was classified as past medical history or a presenting complaint.

Adherence with allocated treatment (FA)

Data listings will be provided, ordered by treatment group and patient ID, of the reasons for:

- Temporary stopping of NAC treatment
- Permanent stopping of NAC treatment
- PP100-01 not being given or PP100-01 being stopped early

Protocol deviations and violations (FA)

A listing of protocol deviations and violations will be provided, ordered by treatment group, patient ID and study time point.

Primary outcome (Safety)

Details of adverse events will be listed, ordered by treatment group, patient ID and start date. The listing will include:

- Event category (as recorded on CRF)
- Start date and time
- Date and time resolved
- Seriousness (yes/no)
- SUSAR (yes/no)
- Intensity (mild/moderate/severe)
- Treatment given in response to AE (yes/no)
- Outcome (recovered/improved/unchanged/deterioration/death)
- Relationship to NAC (unrelated/possibly related/probably related/definitely related)
- Relationship to PP100-01 (unrelated/possibly related/probably related/definitely related)
- Action taken with NAC (none/interrupted/stopped entirely)
- Action taken with PP100-01 (none/interrupted/stopped entirely)
- Expectedness with NAC (expected/unexpected/NA)
- Expectedness with PP100-01 (expected/unexpected/NA)

Concomitant Medication (FA)

Three concomitant medication data listings will be provided, one for medications in the 30 days preceding randomisation; the second for medications recorded as “ongoing” at baseline; and a third for those started on or after the date of consent. Each listing will be ordered by treatment group, patient ID and start date, and will contain: Patient ID; Randomisation date; Category; Medication; Start date; Stop date; Ongoing; Dose & Units; Frequency; Route.

5. Derived variables

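### The 24-hour hold in each dosing cohort starts at recruitment of the first patient allocated to PP100-01, so it can run out with nobody exposed at the new dose

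*Protocol*

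**What the plan says.** Protocol section 6.6.1 describes the start of the hold as follows: "A period of 24 hours will be left between recruitment of the first participant allocated to PP100-01+NAC treatment". The rule applies separately to every cohort. Its end point and its aim are given in these words: "recruitment of the next participant to allow adequate time for early adverse events to be identified". Both ends of the interval are recruitments.

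The same section places allocation at the start: "There will be a randomisation process at entry to the study that will determine treatment allocation within dosing cohort". The table in section 7.2 also puts it in the screening column. PP100-01 comes later. Section 7.1.7 fixes the pre-dose sample at 2 hours after the start of NAC: "Immediately prior to PP100-01 a study specific blood sample will be collected (time 2hr"). Section 7.1.11 gives the dosing window: "PP100-01 treatment should be +/- 10mins of timepoint".

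The plan allows for allocated patients who do not get the bolus:

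- Section 6.6.4 lets patients withdraw at any time.
- SAP section 4.3 has a bolus status for PP100-01 not started.
- SAP section 4.9 lists the reasons for "PP100-01 not being given or PP100-01 being stopped early".

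On replacement, section 6.7 says only: "Any patients that discontinue treatment for a reason other than Dose Limiting Toxicity (DLT) will be replaced". It does not mention the hold.

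**The concern.** The hold exists so that a patient exposed at a new dose can be observed before another is recruited. Its clock starts at an event that comes before exposure and does not guarantee it. If the first allocated patient is never dosed, the rule is formally met after 24 hours with no exposure observed. Under section 6.6.1 an allocated patient stays in the study, so on a literal reading the undosed patient is still the first one allocated, and the replacement does not trigger a new hold.

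This is the only rule in the documents that spaces patients within a cohort. The committee review comes after a whole cohort, and the pause rules in section 10.10 act only once a serious outcome has occurred. Section 13.1 calls the risks of the combination unknown, and section 2.3 lists an immediate fall in blood pressure among the important potential risks. An early event of that kind is what such a hold can reveal.

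**Working it through.** The 24 hours is a design rule, so there is no formula to reproduce. The check has three parts.

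**1. First allocated patient dosed on schedule**

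Inputs: hold of 24 h (6.6.1); dose at d = 2 h ± 10 min after NAC start (7.1.7, 7.1.11). Recruitment time r relative to NAC start is not given; I assume 1 h before to 2 h after.

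Time after the dose within the hold = 24 − (d − r).

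| r (h) | d (h) | Hours after the dose |
|---|---|---|
| −1 | 2.17 | 20.8 |
| 0 | 2.17 | 21.8 |
| 0 | 2.00 | 22.0 |
| 0 | 1.83 | 22.2 |
| 2 | 2.00 | 24.0 |

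The hold therefore covers about 21 to 24 hours after the bolus. A delayed dose shortens this hour for hour.

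**2. First allocated patient not dosed**

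Observed exposure is 0 h, and the 24 hours still elapse. Let p be the probability that an allocated patient is not dosed. The documents give no value, so p is an assumption. The chance that this happens to the first allocated patient in at least one of three cohorts is 1 − (1 − p)³.

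| Assumed p | At least one of three cohorts |
|---|---|
| 1% | 3.0% |
| 2% | 5.9% |
| 5% | 14.3% |
| 10% | 27.1% |
| 15% | 38.6% |

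**3. Chance that two PP100-01 patients are then also recruited within 24 hours of each other**

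Inputs: 24 patients in 6 to 12 months (6.1); 6 of every 8 allocated to PP100-01, which is 75% (6.6.1). Assumptions: arrivals are random at a constant rate, and they are independent of whether the first patient was dosed.

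- Slow accrual: 24/365 × 0.75 = 0.0493 PP100-01 patients per day. The chance of another within 24 h of the first exposed patient is 1 − exp(−0.0493) = 4.8%.
- Fast accrual: 24/182.5 × 0.75 = 0.0986 per day, giving 1 − exp(−0.0986) = 9.4%.

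Combined with non-dosing of the first allocated patient, over three cohorts:

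- p = 5%, slow accrual: 1 − (1 − 0.05 × 0.048)³ = 0.7%.
- p = 15%, fast accrual: 1 − (1 − 0.15 × 0.094)³ = 4.2%.

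Committee pauses between cohorts would make accrual within a cohort faster than these averages. With the rate doubled, the same steps give about 1.4% (0.05 × 0.094 per cohort) to 7.8% (0.15 × 0.179 per cohort).

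**The case against.** The strongest reply is that the gap rarely matters:

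- Section 6.3 excludes patients thought unlikely to complete NAC, and only about two hours separate NAC start from the bolus.
- Recruitment is planned at about one patient every 8 to 15 days, so natural spacing usually does the work of the hold.
- The committee reviews each cohort before the next, and enrolment pauses on the events in section 10.10.
- Section 2.3 reports earlier clinical use of calmangafodipir at the same three doses.
- Section 6.6.1 states its purpose, so a sensible investigator could read the hold as applying to the first patient exposed.

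Most of this stands as a limit on size. None of it changes the start of the clock. The documents are silent on what happens to the hold after a non-dosed first patient, so it is fair to call this an ambiguity to settle rather than a proven failure.

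Two stronger readings of the evidence should be resisted. A reader might cite the SAP section 4.3 count, "Numbers of patients who were randomised but never treated with either NAC or PP100-01", as showing that bolus omission is foreseen. That count concerns patients given neither drug; the apt support is the bolus status in the same section and the listing in SAP section 4.9. A reader might also infer that a reaction during the loading dose leads to PP100-01 being withheld. Section 9.3 describes interruption and restart of the infusion, which points to delay and does not say that PP100-01 is omitted.

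**Conclusion.** The point holds as a conditional defect of low probability. As written, the hold can expire with nobody exposed at the new dose, contrary to its own purpose. It works when the first allocated patient is dosed on schedule.

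A reader might take 39% as the chance of harm, or infer that all six patients at a new dose could be treated without spacing. The documents support neither. The 3% to 39% range rests wholly on an assumed non-dosing rate of 1% to 15%, and it measures an unexposed first patient, not close-together dosing. Six patients dosed together is a logical ceiling that the planned accrual makes implausible. The more relevant figure is about 0.7% to 4% across three cohorts, under assumed non-dosing of 5% to 15% and random arrivals at the planned rate, and somewhat more if accrual within a cohort is faster. It would be lower if non-dosing is rarer than 5%.

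The sponsor wrote the hold knowing the planned accrual, so the protection was judged worth having. Its wording should deliver it.

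**What to change.** Reconcile the trigger in section 6.6.1 with its stated purpose. Attach the existing 24-hour hold to the first participant in each dosing cohort who actually receives PP100-01, and count it from that administration to the recruitment of the next participant. Add to section 6.7 that the hold carries over if the first allocated participant is not dosed. No new interval, dose or clinical rule is proposed.

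The cost is a short protocol amendment, about 2 hours more per cohort in the usual case (24 h against about 22 h after the bolus now), and an occasional extra wait when the first allocated patient is not dosed. No patients or procedures are added.

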6.6.2 Randomisation

The allocation sequence for each dosing cohort will be created using computer-generated random numbers, using blocking to ensure the required 6:2 ratio of NAC+PP100-01:NAC alone. The randomisation list will be held centrally at the Edinburgh Clinical Trials Unit (ECTU) in order to conceal treatment allocations until these are implemented via the ECTU secure web-based randomisation system.

6.6.3 Blinding

This is an open label study without blinding.

6.6.4 Patient Withdrawal

Patients are free to withdraw from the study at any time. If they withdraw from the study, this will be recorded, and data collected to that time point may be used if the patient agrees and the data included in the final analysis. If they withdraw consent to have their data stored, then they will be documented on the study Consort flow diagram as "withdrawn" and their data will not be used in the final analyses. Reasons for withdrawal will be collected if the patient is willing for us to do so, but they do not have to give a reason.

6.7 Patient Replacement

Replacement of patients will be allowed in order to obtain the planned number of evaluable patients in each dosing cohort. Any patients that discontinue treatment for a reason other than Dose Limiting Toxicity (DLT) will be replaced.

7 PATIENT ASSESSMENTS AND DATA COLLECTION

7.1 Description of Assessments

7.1.1 Blood Samples

NAC will be given to all patients arriving to the hospital according to the standard guidelines when paracetamol/acetaminophen overdose is suspected. All patients that arrive to the hospital before 24hrs after POD will be asked if they will participate in the study.

As part of routine clinical care all patients presenting to hospital following a paracetamol overdose will have the following blood tests on arrival to hospital or 4hrs after overdose (whichever is the longer time).

- S-APAP level in serum
- Urea, sodium, potassium and creatinine
- Liver function tests (LFTs) ALT, Bilirubin and ALP
- Clotting screen: INR and Prothrombin time (PT)
- Haemoglobin, White Blood Cells(WBC), Mean Cell Volume (MCV)

Immediately prior to administering PP100-01 a study specific blood sample will be collected (10mL split over serum and plasma) which will measure:

- ALT, bilirubin and alkaline phosphatase (ALP)
- Prothrombin time and INR
- Serum creatinine
- Biomarkers: CK18 and microRNA MiR122, GLDH, mitochondrial DNA and others
- PP100-01 levels

These measurements are part of the sub-study examining novel biomarkers.

As part of routine clinical care there will be blood sampling at 10 hrs and 20 hrs after starting NAC. The following are routinely measured:

- S-APAP level in serum
- Urea, sodium, potassium and creatinine
- Liver function tests (LFTs) ALT, Bilirubin and ALP
- Clotting screen: INR and Prothrombin time (PT)
- Haemoglobin, White Blood Cells(WBC), Mean Cell Volume (MCV)

At these 10hr and 20hr venepuncture episodes study specific blood samples will also be collected (at each time 10mL split over serum and plasma) which will measure:

- Biomarkers: CK18 and microRNA MiR122, GLDH, mitochondrial DNA and others
- PP100-01 levels

